#### 2.3.8.2 SERIOUS ADVERSE EVENTS

#### 2.3.8.2.1 Description

A Serious Adverse Event (SAE) is an adverse event which:

- 1. Led to a death,
- 2. Resulted in life threatening illness or injury,

NOTE: the term "life-threatening" refers to an event in which the patient was at a risk of death at the time of the event; it does not refer to an event which hypothetically might have caused death if it were more severe.

- 3. Resulted in subject hospitalization or prolongation of existing hospitalization,
- 4. Resulted in subject disability or permanent damage or required intervention to prevent permanent impairment/damage.

### 2.3.8.3 UNANTICIPATED ADVERSE DEVICE EFFECTS

#### 2.3.8.3.1 Description

An Unanticipated Adverse Device Effect (UADE) is any serious adverse effect on health or safety or any life threatening problem or death caused by, or associated with, a device, if that effect, problem, or death is not identified in nature, severity, or degree of incidence in this Protocol; or any other unanticipated serious problem associated with a device that relates to the rights, safety, or welfare of the subjects.

### 2.3.8.3.2 Reporting

SAEs and UADEs must be reported to the Sponsor, as soon as possible, but in no event later than 10 working days after the Investigator first learns of the event. SAEs and UADEs must also be reported to the approving IRB per the IRB's reporting requirements.

#### 2.3.8.4 POTENTIAL RELATIONSHIP OF ADVERSE EVENTS

Investigators will be asked to assess the potential relationship of the adverse event to the implanted device and to the procedure and classify the causality of the event according to the following definitions.

- Definitely Related: An adverse event that has a strong causal relationship. An adverse event that follows a strong temporal relationship to the use of the device or the procedure, follows a known response pattern, and cannot reasonably be explained by known characteristics of the subject's clinical state or other therapies.
- Probably Related: An adverse event that potentially has a causal relationship. The adverse event has a reasonable temporal relationship to the use of the device or the procedure and alternative etiology is less likely compared to the potential relationship to the use of the device or the procedure.
- Possibly Related: An adverse event that potentially has a causal relationship. The adverse event has a reasonable temporal relationship to the use of the device or the procedure but alternative etiology is equally likely compared to the potential relationship to the use of the device or the procedure.
- Not Related: An adverse event without any apparent causal relationship. The adverse event is due to the underlying disease state or is due to concomitant medication or therapy not related to the use of the device or the procedure.

• Unknown Relationship: If the adverse event cannot be determined to have a causal relationship, it will be classified as unknown.

#### 2.3.8.5 ASSESSMENT OF SEVERITY

- Mild: event/symptom is transient and well tolerated by the patient.
- Moderate: event/symptom causes discomfort and interferes with routine activities of the patient.
- Severe: event/symptom interferes considerably with the routine activities of the patient or causes inability to work.
- Life-Threatening: refers to an event in which the patient was at a risk of death at the time of the event; it does not refer to an event which hypothetically might have caused death if it were more severe.

### **2.3.8.6 CLINICAL EVENTS COMMITTEE**

The Clinical Events Committee ("CEC") will adjudicate all adverse events. This will include all UADEs, SAEs, secondary surgeries at the index and adjacent levels, adverse events determined to be "severe", and adverse events deemed definitely, probably and possibly related or with an unknown relationship to the device or procedure. The CEC will review investigator assigned neurological status at 60 months for the Simplify Disc group onlyto determine if neurological status has improved, maintained or declined compared to baseline in the IDE study.

The CEC may determine neurologic status has declined based on changes including:

- Motor Assessment: shift of -1.
- Sensory Examination: shift from normal to abnormal; abnormal to
- increased abnormality.
- Reflex Response: shift from Normal to anything else; hyporeflexive to
- absent; hyporeflexive to hyperreflexive or hyperreflexive to hyporeflexive.
- Clumsiness, Atrophy, Cramping, Spasms and Numbness: shift from
- absent to present.
- Dysphagia (difficulty swallowing) and Dysphonia (difficulty with producing
- sounds resulting in hoarseness, weakness, harshness, roughness and/or
- breathy sound): any worsening.

- Myelopathic Gait Abnormality Class: any worsening
- Assessment: Does the CEC agree with the investigator assessment

The CEC will also adjudicate all protocol deviations. The CEC will consist of three spine surgeons who are not affiliated with the Sponsor or who are not participating in the study. The CEC charter is used for adjudication of both Simplify Disc and historical control ACDF patients. The recommendations of the CEC override the investigator's classification and become part of the clinical trial data set.

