## 2.3.6.2 STUDY EVALUATIONS, PROCEDURES AND ASSESSMENTS

Follow-up evaluations annually at Month 36, Month 48, and Month 60 will include:

- AP and lateral X-rays (plain films);
- Flexion-extension X-rays (used to determine range of motion);
- Lateral bending films (Simplify Disc only);
- Radiographic core lab evaluations;
- Dysphagia Handicap Index (Simplify Disc only);
- NDI assessment;
- SF-12v2 Health Survey (Simplify Disc only);
- VAS pain assessments (neck and arm; neck, left arm and right arm (Simplify Disc only));
- Neurologic evaluation;
- Study related medication status (Simplify Disc Only);
- Work status;
- Treatment satisfaction assessment and
- Adverse events as defined by Section 2.3.8 of this protocol.
- •

Neurologic status will be evaluated by a qualified evaluator, who may be an MD, DO, an RN or a PA. The neurologic evaluation will include a motor and sensory assessment, reflex responses and the determination of the presence or absence of dysphagia, dysphonia, clumsiness, foot drop, atrophy, cramping, muscle spasms, numbness and gait abnormality.

Muscle strength will be graded for the deltoid (C5), biceps (C6), and triceps (C7) according to a 6point scale where 0 = no movement, 1 = trace of muscle contraction; 2 = active movement without gravity; 3 = active movement against gravity; 4 = active movement against gravity/resistance; and 5 =normal response.

Study related medication status will include only medications taken or administered for the following

- Pain (any type);
- Inflammation (any type);

- Muscle relaxation;
- Numbness &/or tingling;
- Hormonal replacement therapy and
- Other medications related to or given for the subject's spinal condition.

All radiographic endpoints will be evaluated independently by one core laboratory.

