#### 2.3.6.2.3 Study Completion, Termination or Loss to Follow-up

Simpliy Disc subjects are expected to remain in the study until the 60 months post implantation assessment. The study completion/ termination evaluation will be made at the 60 months assessment, or at earlier time point if the subject withdraws or is withdrawn from the study.

Subjects may be withdrawn from a clinical study early due to withdrawal of Informed Consent, loss to follow-up, or Investigator medical decision. Any premature termination from the study will be documented, including the primary reason for withdrawal. In the event of a secondary index surgery requiring removal of a spinal system, every effort will be made to retrieve the explanted device for analysis. The instructions for the surgical technique for device removal of the Simplify Disc are included in the Study Manuals. Any subjects with a device removal of the Simplify Disc or who have any other secondary index surgery will be discontinued from the study after the next follow-up study visit.

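### The CEC determines neurological status only at Month 60, so subjects who leave earlier get no determination, and its decline list omits foot drop and uses a gait class the examination does not define

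*Combined protocol and SAP*

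**What the plan says.** **Examination.** Section 2.3.6.2 sets the schedule ("Follow-up evaluations annually at Month 36, Month 48, and Month 60 will include") and includes a neurologic evaluation. Besides motor, sensory and reflex testing, the evaluator records the "presence or absence of dysphagia, dysphonia, clumsiness, foot drop, atrophy, cramping, muscle spasms, numbness and gait abnormality". Muscle strength is graded for deltoid, biceps and triceps only.

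**Early exit.** Section 2.3.6.2.3 places the completion or termination evaluation at 60 months, "or at earlier time point if the subject withdraws or is withdrawn from the study". It also discontinues any subject with device removal or another secondary index surgery once the next follow-up visit has taken place.

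**Adjudication.** Section 2.3.8.6 says: "The CEC will review investigator assigned neurological status at 60 months for the Simplify Disc group". The CEC classes status as improved, maintained or declined against the IDE baseline, and its view overrides the investigator's. The guide to decline opens with "The CEC may determine neurologic status has declined based on changes including". One line begins "Clumsiness, Atrophy, Cramping, Spasms and Numbness: shift from" and covers a change from absent to present. Another reads "Myelopathic Gait Abnormality Class: any worsening". Foot drop is not on the list.

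**The concern.** The stated purpose of the study is 5-year safety and efficacy, and the CEC's neurological determination is an independent check within the safety section. Tying it to Month 60 restricts it to subjects who stay to the end. Those who leave early are not a random subset: the protocol itself removes subjects who have secondary index surgery, a group in which neurological change is of obvious interest. If early leavers did worse, the adjudicated decline rate at Month 60 would be too low, although the examinations needed to show this may already be on file.

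The second issue is the fit between what is examined and what is adjudicated. An item recorded at every visit but missing from the guide is left to the discretion of each CEC review. A graded item that the examination records only as present or absent may not be gradable for someone who already had the finding at baseline.

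**Working it through.** **1. How many subjects could lack a Month 60 status.** Section 2.3.7.5 gives 142 Simplify Disc subjects and 85% expected to be available at year 5.

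- 0.85 × 142 = 120.7, which rounds to the plan's 121. The figure reproduces.
- 142 − 121 = 21, and 21/142 = 14.8%.

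This reads availability at year 5 as having a Month 60 visit. The section does not say how subjects discontinued after secondary surgery are counted.

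**2. How many of the 21 were examined earlier in this study.** The documents do not say. Section 2.3.4 describes up to 142 eligible subjects who must consent, and section 2.3.4.2 excludes those who do not. Some of the 21 may never enrol, or may leave before Month 36. The number with an examination that the CEC would not review therefore lies between 0 and 21. The documents give no decline rate for either group, so no effect on the reported rate can be calculated.

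**3. Examination against decline list.** Section 2.3.6.2 records nine items as present or absent.

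| Examined item | In the CEC list? | How the list treats it |
|---|---|---|
| Clumsiness, atrophy, cramping, spasms, numbness (5) | Yes | Absent to present |
| Dysphagia, dysphonia (2) | Yes | Any worsening |
| Gait abnormality (1) | Yes | Any worsening of a class |
| Foot drop (1) | No | Not named |

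The list names 5 + 2 + 1 = 8 of the 9. The motor item does not make up for foot drop, because the three graded muscles are all in the upper limb. Myelopathy is within the study population (sections 2.3.1 and 2.3.7.1), so a lower-limb sign is relevant.

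For gait, a change from absent to present is a worsening and fits the list. A subject with abnormal gait at baseline stays present whatever happens, and section 2.3.6.2 defines no class by which to record further loss.

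**4. Other routes to the CEC or the tables.**

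- The CEC adjudicates all adverse events without restriction by visit (section 2.3.8.6). This depends on the investigator judging the change clinically significant and reporting it (section 2.3.8.1).
- Deterioration is counted at each time point (section 2.3.7.8.1), but for pain, motor and sensory status only. Reflexes, gait and foot drop are not among those items.

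What remains uncovered is a decline in a subject who leaves before Month 60 that was not reported as an adverse event.

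**The case against.** The case for leaving the text alone is substantial. Month 60 is the plan's stated evaluation point. Investigators ask about adverse events at every visit (section 2.3.7.11), and every reported event reaches the CEC. Motor and sensory deterioration is tabulated annually. The decline list is permissive and open-ended, so foot drop is unnamed rather than excluded, and three spine surgeons would hardly ignore it. The CEC charter and case report forms are not among the documents and may define the gait class or the handling of early exits.

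Most of this stands, and it rules out several stronger readings that a reader might infer:

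- **Worsening gait is missed altogether.** It is on the list, and new onset qualifies. Only further loss from an abnormal baseline is in doubt.
- **Worsening dysphagia cannot be registered.** The Dysphagia Handicap Index is collected annually and compared with the IDE baseline.
- **A motor loss of more than one grade would not count as decline.** The list's motor entry is a matter of wording, and no sensible reader would take it that way.
- **Earlier declines are never reviewed.** Reported adverse events are adjudicated whenever they occur.
- **Adjudicated decline is a named safety endpoint.** The readable text describes a CEC task and does not list it as an endpoint.

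The objection does not remove the gap for early leavers. The CEC's power to override the investigator shows that its review is meant to add to investigator reporting, so reliance on reported events is not equivalent. If the charter already covers early exits and the gait class, the protocol need only say so.

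**Conclusion.** The point holds as a cheap improvement to safety ascertainment. As written, a Simplify Disc subject without a Month 60 visit has no CEC neurological status, including one discontinued after secondary index surgery unless the next visit happens to be Month 60. On the plan's 85% retention assumption this is up to 21 of 142 subjects, of whom 0 to 21 have an earlier examination in this study. The likely direction is a decline rate that is too low, if early leavers fare worse. That is a reasonable expectation but not something the documents show, and any numerical shift in the rate would rest on invented inputs.

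Foot drop and the gait class are smaller mismatches between sections 2.3.6.2 and 2.3.8.6. A reader might infer a threat to the main result. There is none: neurological status is not part of the Month 60 composite (sections 2.3.2 and 2.3.7.1), so the non-inferiority and superiority tests are untouched.

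**What to change.** - In section 2.3.8.6, for subjects with no Month 60 visit, have the CEC also review the last available or termination neurological evaluation. Report decline both at Month 60 and at last available visit, stating the number of subjects behind each. The two should be kept apart because the second mixes follow-up times.
- Add foot drop, absent to present, to the decline list.
- Reconcile the gait item between sections 2.3.6.2 and 2.3.8.6 so that the scale recorded is the scale adjudicated. Where the IDE baseline holds only presence or absence, limit the item to new onset.
- If the CEC charter already settles any of these, cite it in the protocol.

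The cost is wording in the protocol and charter, possibly a small case report form edit for gait, and a small amount of extra CEC review: at most 21 further subjects on the plan's retention assumption. No new visit or committee is needed. CEC review of every subject at every annual visit would also close the gap, but it is optional and could be limited to subjects with any change from baseline.

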# 2.4 RISK ANALYSIS

### 2.4.1 RISKS

No physical risks are anticipated as a result of participation in the long-term follow-up study. The amount of radiation exposure to subjects is relatively small.

Subjects may require additional surgery at the treated spinal level:

- Reoperation any surgical procedure at the index level that *does not involve* modification, addition or removal of any components of the device" in the postoperative or follow-up period.
- Revision any procedure in the postoperative or follow-up period that adjusts modifies or removes part of the original implant configuration *with or without* replacement of a component – may include adjusting the position of the original configuration in the postoperative or follow-up period.
- Removal a procedure where the entire device is removed with or without replacement of the device in the postoperative or follow-up period.
- Supplemental fixation a procedure in which additional instrumentation not under study is implanted (e.g., supplemental placement of a rod/ screw system)

Risks associated with the use of both the Simplify Disc and control spinal systems are expected to be comparable. All secondary index surgeries will be regarded as failures and reported accordingly.

# 2.5 STUDY MONITORING

### 2.5.1 MONITORING ORGANIZATION

Study monitoring functions, with assistance from the Sponsor or designee for any study training visits, will be performed by an independent clinical monitoring organization, in compliance with recognized Good Clinical Practices as applied to medical device studies, FDA's IDE guidance documents, and as outlined in 21 C.F.R. § 812.43(d) and 21 C.F.R. §812.46. The monitoring organization will act as the Clinical Monitor. The major function of the Clinical Monitor is to observe and assess the quality of the clinical study.

In addition to ensuring adequate communication between the investigators and the study Sponsor, the monitor's duties include on-site and remote visits and review of study documents and results. The monitoring organization has been provided with appropriate training regarding the Simplify Disc and will operate under written procedures to ensure compliance with the protocol.

## 2.5.2 MONITORING VISITS

Monitoring visits include a pre-study visit, periodic visits and a close-out visit at the end of the site's participation in the study. The pre-study visit, which may be performed by the Sponsor or designee, will be conducted remotely and is intended to provide an opportunity to review the Study Plan and associated study documents with the Investigator. and to ensure that the Investigator has IRB approval and all required documentation prior to initiating the post approval study:

Periodic visits are intended to assess adherence to the Study Plan, maintenance of Records and Reports; and provides for review of source documents for accuracy, completeness, and legibility. During these periodic visits, the monitor is required to assess the progress of the study toward meeting study objectives; to identify any concerns that stem from observations of device performance and/or review of the subject records, study management documents or Informed Consent documents; to ensure that the site has assessed adverse events according to protocol requirements; and to ensure accountability of all subjects. A periodic visit may be performed on-site or remotely.

The monitor's final visit at completion of the study is intended to ensure that all the data have been properly completed and to have a closing meeting with the Investigator and his/her staff members to discuss findings, observed problems and potential solutions.

Reports of the monitoring visits will be made by the monitor and should include a means of tracking resolution of concerns, completion of appropriate follow-up activities, completion of assigned tasks, and any necessary corrective actions. At the close of the study, a final report will be prepared by the monitor for each site.

# 2.5.3 DATA COLLECTION

Data will be compiled using an Electronic Data Capture system operated by the Independent Monitoring Organization. The Clinical Monitor will verify that appropriate data are recorded for all study subjects for whom Informed Consent is obtained; and that no study evaluations are completed without Informed Consent. Documentation will be provided for study subjects who choose to terminate study participation and for subjects terminated by their physicians. A full explanation of the reasons for non-participation will be provided.

Data will be reviewed to identify inconsistent or missing data, SAEs, and UADEs. Data problems will be addressed in calls to the study sites and during site visits. Electronic Case Report Forms and data files will be secured to ensure confidentiality. Quality assurance procedures are designed to ensure that complete, accurate and timely data are submitted, that protocol requirements are followed, and that complications and adverse events are reported as required under Section 2.2.6.1 and Section 2.2.7 of this protocol.

## 2.5.4 REVIEW OF STUDY DOCUMENTS

The monitor will review completed data forms and study documentation for accuracy, completeness, and protocol compliance. Although not limited to these, the following documents will be audited:

- The Clinical Trial (Investigator) Agreement signed by the investigator, indicating his/her agreement to participate in the investigation and willingness to comply with all study requirements.
- Electronic Case Report Forms will be reviewed for errors, omissions, internal consistency, and signature and dates in the appropriate sections. The monitor will assume responsibility for any follow-up activities that result from review of these forms. Subject Informed Consent documents will be reviewed for completeness.
- Study Monitor Reports by a site monitor will be reviewed by the senior monitor. The monitor will assume responsibility for any corrective action.

## 2.5.5 MEDICAL MONITORING

NuVasive, Inc. has appointed a qualified spine surgeon to oversee all medical monitoring issues. Duties of the Medical Monitor include, but are not limited to:

- Being available to investigators for questions regarding adverse event reporting;
- Being available to the FDA for medically related questions regarding this clinical study.
- May attend CEC meetings as a NuVasive, Inc Official.

# 2.5.6 ROLE OF CO-PRINCIPAL INVESTIGATORS

NuVasive, Inc. has appointed experienced spine surgeons to oversee all Co-Principal Investigator issues. Duties of the Co-Principal Investigators include, but are not limited to:

- Review the protocol;
- Being available to investigators for questions regarding protocol criteria and surgical related questions;
- Being available to the FDA for medically related questions regarding this clinical study.

# 2.5.7 DISPOSITION OF ANY EXPLANTED STUDY DEVICES AND DATA

Should it be necessary to explant the Simplify Disc, NuVasive, Inc. shall provide surgical instructions in the Simplify Disc Surgical Technique Guide and a device retrieval kit and instructions detailing the appropriate procedure for handling explanted devices. All Simplify Disc explant procedures will attempt to collect tissues adjacent to the device (e.g., bone-implant interface) for independent histopathological and wear examination.

All information received by the study Sponsor or authorized agents of the study Sponsor pertaining to subjects will be held on a confidential basis. This information may be subject to audit by regulatory authorities where appropriate. Authorized agents of the study Sponsor will have the right to inspect and copy information in subject files. Copies will be blinded to replace subject identifying information with subject identifiers.

